8.10 Overdose

If the investigator believes that there is a drug overdose (e.g., a single oral dose of more than 4000 mg [16 capsules]) during the clinical study, the investigator should treat the event as a SAE and report it promptly, even if the occurrence is not included in the definition described above. Overdose should be recorded on the AEs page of the eCRF form and noted on the original record.

Nomenclature HTD1801/Clinical Phase II Protocol No.: HTD1801.PCT103

9. DATA MANAGEMENT

9.1 Data Management Process

The data management of this study should be completed by the CRO data department to ensure the authenticity, integrity, privacy and traceability of clinical study data. Detailed data management procedures will be described in a separate data management plan.

Protocol No.: HTD1801.PCT103

9.2 Data Acquisition

Data will be collected through an electronic data capture (EDC) system. Subject data is entered into the eCRF by the investigator or by an investigator-authorized on-site staff. The investigator or the investigator-authorized staff will receive appropriate training and take appropriate information security measures prior to site start-up or data entry. The investigator should supervise the data collection at the study site. The investigator should ensure that all clinical study data are obtained from clinical study source documents and study records, and are accurate, complete, readable and timely. Source data should be attributable, legible, contemporaneous, original, accurate, complete, consistent, and durable. There should be traces for modification of the source data, without concealing the original data, and the reason for the modification should be recorded.

Unless otherwise specified, eCRF will only be used as a form for collecting data, rather than the raw data. Source documents refer to the original records, documents and data generated in this study, such as hospital medical records, medical images, laboratory records, memos, subject diaries or evaluation forms, drug dispensing records, automatically recorded data from instruments, X-rays, subject's documents, and study-related documents and records kept by pharmacies, laboratories, and medical technology departments, including certified copies. Source documents include source data, which can be present in paper or electronic forms. To avoid differences in assessments between assessors, it should be ensured that the baseline and all follow-up visit assessments of efficacy and safety for the same subject are completed by the same assessor.

The investigator is responsible for maintaining all original documents and ensuring that they are monitored by a clinical research associate (CRA) at each visit. In addition, the investigator should submit a complete eCRF for each subject participating in the study, regardless of the study duration of the subject. All supporting documents (such as laboratory or site records) submitted with the eCRF should be carefully verified for study number and subject number, and all private personal information (including subject names) should be removed or made illegible to protect subjects' privacy.

9.3 Database Design

The eCRF is constructed in the EDC system by the CRO data department, and this process should meet the requirements of Part 11, FDA 21 CFR. The database shall manage data traces, such as system login, data entry, modification, and deletion. The establishment of the database shall adopt the Clinical Data Interchange Standards Association (CDISC) standard as far as possible.

The Sponsor should have written procedures to ensure that changes to the eCRF are necessary, documented, and approved by the investigator. Investigators should keep relevant revision and correction records.

9.4 Data Entry and Change

All input data are in Simplified Chinese. The investigator or the investigator-authorized field staff should fill in and modify the eCRF in accordance with the instructions provided by the CRO data department, while CRA does not have this authority. The investigator should ensure that the data in eCRFs and other reports is accurate, complete, definite and timely. All data should be entered into the EDC during the visit or as soon as possible after the visit, and the data entry should strictly

follow the principle of "what you see is what you record". The EDC must be kept up to date to ensure that it reflects the latest developments in subjects. If certain assessments are not performed during the study, or if certain information is unavailable, inapplicable, or unknown, the investigator or the investigator-authorized field staff should record it in the eCRF.

Protocol No.: HTD1801.PCT103

The data in the eCRF will be handed over to the data server. The investigator must review the data to ensure the accuracy and correctness of all input data, and electronically sign the verified data. The signed information (including the date of signature) will be saved in the audit track and cannot be changed.

The data in the eCRF should be the same as the source document, and if there is any inconsistency, a reasonable explanation should be given. For any corrections or modifications made to the eCRF, the investigator or the investigator-authorized field staff should make the original record legible, keep a rack of the modification, explain the reasons if necessary, and sign and date the modification. Changes to data that have been approved should be re-signed electronically by the investigator.

9.5 Data Verification

According to the finalized data verification plan, the data administrator will set up data logic verification programs in the EDC system.

After the data is entered into the EDC system, the data will be validated by computer logic verification and manual verification to ensure the data is logic, consistent and accurate.

After the data is entered into the EDC system, if there is any data that does not conform to logics, the system logic verification will start operation and trigger a query. These queries should be reviewed and answered by the investigator or the investigator-authorized staff. When the logical verification is no longer valid due to the updated data, the data query should be closed immediately; when the study site confirms the data and provides a reply, the data administrator should review and reply to the information. If the reasons provided by the study site are reasonable, the data query should be closed; if the data problem is not resolved, the data administrator can continue to communicate with the study site by continuing to add the data query until the data problem is finally resolved.

The subject data list/report is generated by programming to support manual data verification throughout the study. When there is data that needs to be clarified/verified/confirmed by the investigator, manual queries can be added to the EDC system, and these queries will be manually closed after the data is corrected or confirmed. The queries will be recorded in the audit track of the EDC system, including the operator's name, time and date.

The data administrator should ensure that all queries are resolved before the database is locked, and the investigator should complete all electronic signatures in the EDC system to ensure the integrity and accuracy of the subject data in the EDC system.

9.6 Medical Coding

The data administrator of the CRO Data Department is responsible for the medical coding for this study. Coding includes medical history, AEs, prior/concomitant medication, and prior/concomitant non-drug therapy.

Prior medical history and AEs will be coded according to the Medical Dictionary for Regulatory Activities (MedDRA) (latest version), and submitted in System Organ Class (SOC) and Preferred Terms (PTs). Prior medications and concomitant/concomitant medications, etc., will be coded using the World Health Organization Drug Dictionary (WHO DD) (latest version), all in the Sponsor-confirmed version.

During the coding, any failure in data coding due to improper, inaccurate, and ambiguous medical terminology will be sent to the investigator for verification and confirmation in the form of query by the data administrator.

Protocol No.: HTD1801.PCT103

Before the database is locked, the data administrator will send a medical coding report to the Sponsor for review by the Sponsor.

9.7 Data Locking

After the established database is reviewed and confirmed to be correct, the principal investigator, Sponsor, and statistician will jointly decide to lock the database, and the data administrator will lock the database in the EDC system. In principle, no further changes are allowed to the locked database. If the data that should be modified is found after the data is locked, the database can be modified with approval by the principal investigator, Sponsor, statistician and data administrator, and written records and signatures of all parties should be preserved.

10. STATISTICAL CONSIDERATIONS

10.1 General Principles

All statistical analyses in this study are performed using SAS 9.4 or above statistical software.

Protocol No.: HTD1801.PCT103

The subject information, efficacy data, safety data and other study endpoint data should be statistically described by treatment group. Statistics used include number of cases (missing cases), mean (two-sided 95% confidence interval, if necessary), median, standard deviation, minimum and maximum for consecutive variables; number of cases (missing cases), frequency (two-sided 95% confidence interval, if necessary), percentage, etc. for categorical variables.

Unless otherwise specified, the significance level of the two-sided test is 0.05. The inter-group differences are considered statistically significant if the P for the inter-group comparison is < 0.05.

The missing values in the raw data are not filled, and when the sensitivity analysis of the efficacy and the judgment of the occurrence time of the safety event are performed, the processing method of the missing values in the raw data should be explained in detail in the statistical analysis plan (SAP).

Unless otherwise specified, the baseline is defined as the last valid measurement before the first dose of investigational drug after enrollment.

The statistical analysis plan will be finalized before the database is locked. After the database is locked, the changes in the SAP will be explained in a special section of the statistical analysis report.

10.2 Determination of Sample Size

Assuming a change from baseline in HbA1c of -1.1%, -1.4%, and -0.4%, respectively, with 12-week treatment in the 2 test groups (HTD1801 capsules 500 mg BID, and HTD1801 capsules 1000 mg BID) and placebo group, a pooled standard deviation is 1.1%, and the α level is 0.05 (two-sided). 81 subjects (27 subjects in each group) can provide 90% power to test for the statistical difference between HTD1801 capsules 1000 mg BID and placebo group, and 63% power to test the statistical difference between HTD1801 capsules 500 mg BID and placebo group. Since it is a Phase II exploratory study, alpha correction is not considered. Given the dropout rate of approximately 20%, 99 subjects are planned to be enrolled in the study (33 subjects in each group).

10.3 Statistical Analysis Population

Full analysis set (FAS): According to the principle of Intention to Treat (ITT), including all subjects who have been randomized in the study and used the investigational drug at least once.

Per-protocol set (PPS): Including all subjects in the FAS population with good compliance and no serious protocol violations. FAS and PPS are used in the efficacy analysis.

Safety set (SS): Including all subjects who have been randomized and used the investigational drug at least once following by at least one subsequent safety assessment.

Pharmacokinetic set (PKS): Including all subjects who have been randomized, used the investigational drug at least once and had at least one valid PK measurement.

10.4 Statistical Analytical Procedures

10.4.1 Subject Disposition

The information on subjects who failed in the screening should be described, including the number of cases screened, the number of cases failed in the screening, and the reasons for screening failure.

The number of cases (percentages) are used to describe the subject enrollment, completion, and withdrawal, and the reasons for withdrawing from the study.

Protocol No.: HTD1801.PCT103

The inclusion of subjects into each analysis set should be summarized.

10.4.2 Demographic and baseline characteristics

All demographics and baseline indicator should be analyzed based on the FAS. Demographic variables and baseline characteristics will be summarized by treatment group.

Descriptive statistics (number of subjects, mean, standard deviation, minimum, median, and maximum) should be used for continuous variables, and frequencies and percentages should be calculated for categorical variables.

Details will be described in the Statistical Analysis Plan.

10.4.3 Primary efficacy analysis

The efficacy analysis is mainly based on the FAS, and the statistical analysis is based on the PPS. The efficacy analysis is mainly based on the therapy strategy, with the on-treatment strategy as the sensitivity analysis.

The primary efficacy endpoint is the change in HbA1c from baseline with 12-week treatment. For the primary efficacy endpoint, the mixed model repeated measures (MMRM) for repeated measurement data is used for analysis, with the change in HbA1c from baseline as the dependent variable, the treatment group, measurement time point, random stratification factor (CAP≥274 dB/m or CAP < 274 dB/m) as the independent variables, and subjects' baseline HbA1c as a covariate. Judgments are made based on model-adjusted least-squares means between-group differences. Sensitivity analysis is performed using an analysis of covariance (ANCOVA) model with the last measurement carried forward (LOCF) for subjects who withdrew from the study before 12 weeks.

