7. EFFICACY EVALUATION

7.1 Primary Efficacy Endpoint:

Changes in HbA1c from baseline with 12-week treatment.

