10.4.4 Secondary efficacy analysis

Secondary endpoints are as follows:

- 1. Percentage of subjects with HbA1c < 6.5% at Week 8 and 12.
- 2. Percentage of subjects with HbA1c < 7% at Week 8 and 12.
- 3. Changes in fasting blood glucose from baseline at Week 4, 8, and 12.
- 4. Changes in postprandial blood glucose from baseline at Week 8 and 12.
- 5. Changes in fasting insulin level from baseline at Week 4, 8, and 12.
- 6. Changes in postprandial insulin level from baseline at Week 8 and 12.
- 7. Changes in fasting C-peptide from baseline at Week 4, 8, and 12.
- 8. Changes in postprandial C-peptide from baseline at Week 8 and 12.
- 9. Changes in serum ALT, AST, GGT, and TBIL from baseline at Week 4, 8, and 12.
- 10. Changes in CAP measured by liver transient elastography from baseline with 12-week treatment.
- 11. Changes in C-reactive protein from baseline with 12-week treatment.
- 12. Changes in serum LDL-C, HDL-C, TG, and TC from baseline at Week 4, 8, and 12.

- 13. Changes in body weights of subjects from baseline at Week 4, 8, and 12.
- 14. Changes in medication for blood lipid control in subjects from baseline with 12-week treatment.

Protocol No.: HTD1801.PCT103

For the measurement data in the secondary efficacy endpoints, the same analysis method as the primary efficacy endpoints is used, with the random stratification factors in the model: CAP and HbA1c; for the enumeration data in the secondary efficacy endpoints, invalid filling is applied and the CMH method is used for inter-group comparison, with the random stratification factors in the model: CAP and HbA1c.

Study Objectives	Endpoints	Estimated Objective	

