Primary objective: to evaluate the effect of HTD1801 on glycemic control in T2DM patients.	Primary endpoint: changes in HbA1c from baseline with 12-week treatment.	Primary Estimated Objective Population: according to the ITT principle, including all subjects who have been randomized in the study and used the investigational drug at least once. Therapy: randomly assigned therapy (see Section 4.1 for details) and possible salvage therapy (see Section 3.3.2 for details) Endpoint: see the left column Concomitant event and treatment strategies: for concomitant event of the salvage therapy, the therapy strategy should be applied, i.e., the data after salvage therapy should also be included in the analysis Summary at population level: the least-squares means inter-group differences should be calculated using MMRM and the ANCOVA model of LOCF (see Section 10.4.3 for details) Secondary Estimated Objective Population: according to the ITT principle, including all subjects who have been randomized in the study and used the investigational drug at least once Therapy: randomized therapy (see Section 4.1 for details) and possible salvage therapy (see Section 3.3.2 for details) Endpoint: see the left column Concomitant event and treatment strategies: for concomitant event of the salvage therapy, the on-treatment strategy should be applied, i.e., the data after salvage therapy should also be included in the analysis Summary at population level: the least-squares mean inter-group differences should be calculated using MMRM and the ANCOVA model of LOCF (see Section 10.4.3 for details)	

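### The primary MMRM has no treatment-by-visit term, so its treatment difference blends Week 8 and Week 12 and is not the 12-week effect named as the primary endpoint.

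*Protocol*

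**What the plan says.** Section 7.1 defines the primary endpoint as "Changes in HbA1c from baseline with 12-week treatment", and Section 10.4.3 repeats it. Section 10.2 sizes the trial on assumed 12-week changes of -1.4, -1.1 and -0.4 points (1000 mg BID, 500 mg BID, placebo) with SD 1.1.

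Section 10.4.3 specifies the MMRM "with the change in HbA1c from baseline as the dependent variable, the treatment group, measurement time point, random stratification factor" (CAP at or above 274 dB/m, or below) "as the independent variables, and subjects' baseline HbA1c as a covariate". The decision rule is: "Judgments are made based on model-adjusted least-squares means between-group differences". No interaction is listed and no visit is attached to the contrast. The legible part of the synopsis gives the same terms. The estimand table in Section 10.4.4 also names no visit and refers back: "the least-squares means inter-group differences should be calculated using MMRM and the ANCOVA model of LOCF (see Section 10.4.3 for details").

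The study process table and Sections 4.3.5 to 4.3.7 schedule post-baseline HbA1c at V6 (Week 8) and V7 (Week 12), not at V5 (Week 4). For continuous secondary endpoints, many of them defined separately at Weeks 4, 8 and 12, Section 10.4.4 says "the same analysis method as the primary efficacy endpoints is used, with the random stratification factors in the model: CAP and HbA1c".

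**The concern.** With treatment and visit as main effects only, the fitted treatment difference is the same number at every visit. Asking the software for the least-squares means difference at Week 12 would return that same number. The primary analysis therefore does not estimate the quantity that Sections 7.1 and 10.2 are about unless the effect is already complete at Week 8, which the protocol neither states nor justifies.

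Three things are at stake:

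- **Effect size by dose.** Section 4.1 calls this a proof-of-concept and dose-range finding study, so the size of each dose's effect matters as well as its significance. If the effect is still growing between Weeks 8 and 12, both doses are understated.
- **Secondary endpoints.** The additive model cannot produce separate between-group differences at Weeks 4, 8 and 12. CAP and C-reactive protein, which have a single 12-week endpoint, are less affected.
- **Sensitivity analysis.** The LOCF ANCOVA compares last values, which are Week 12 values for completers. A disagreement with the MMRM could reflect different targets rather than missing data.

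**Working it through.** **1. The plan's own figure.** Inputs from Section 10.2: n = 27 per arm, SD 1.1, two-sided alpha 0.05, differences -0.4 - (-1.4) = 1.0 and -0.4 - (-1.1) = 0.7.

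Normal approximation: power = Φ(δ / (SD·√(2/n)) - 1.96), with 1.1 × √(2/27) = 0.2994.

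- 1000 mg BID: 1.0/0.2994 = 3.340, power 91.6% (two-sample t-test 90.6%; plan 90%).
- 500 mg BID: 0.7/0.2994 = 2.338, power 64.7% (t-test 63.1%; plan 63%).

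The plan's figures reproduce, and they are for a single comparison at Week 12.

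**2. What the additive model estimates.** Let d8 and d12 be the arm differences at the two visits, s8 and s12 the visit SDs and ρ the within-subject correlation. With complete data and an unstructured covariance, the common treatment effect is w8·d8 + w12·d12, where

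w8 = (s12² - ρ·s8·s12) / (s8² + s12² - 2ρ·s8·s12), and w12 = 1 - w8.

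**3. Illustrative case.** Assumptions not in the protocol: s8 = 1.0, ρ = 0.8, Week 8 effect = 80% of Week 12. From the plan: s12 = 1.1.

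- ρ·s8·s12 = 0.88
- w8 = (1.21 - 0.88) / (1.00 + 1.21 - 1.76) = 0.33/0.45 = 0.73; w12 = 0.12/0.45 = 0.27
- 1000 mg BID: 0.73 × 0.80 + 0.27 × 1.00 = 0.85 instead of 1.0
- 500 mg BID: 0.7 × 0.853 = 0.60 instead of 0.70

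A simulation of 4,000 trials with 27 per arm and the covariance estimated gave a mean of 0.852 from the additive model, against 1.000 for the Week 12 contrast of the interaction model.

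**4. Range.** s12 = 1.1 throughout. Power is by normal approximation with 27 complete subjects per arm, using the variance of the weighted average, (s8²·s12² - (ρ·s8·s12)²) / (s8² + s12² - 2ρ·s8·s12).

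| s8 | ρ | Week 8 effect, % of Week 12 | Weight Week 8 / Week 12 | Estimate, true 1.0 | Estimate, true 0.7 | Power 1000 mg / 500 mg |
|---|---|---|---|---|---|---|
| 1.1 | 0.8 | 60 | 50 / 50 | 0.80 | 0.56 | 80.4% / 50.5% |
| 1.1 | 0.8 | 80 | 50 / 50 | 0.90 | 0.63 | 88.7% / 60.2% |
| 1.1 | 0.8 | 90 | 50 / 50 | 0.95 | 0.665 | 91.7% / 64.9% |
| 1.1 | 0.8 | 100 | 50 / 50 | 1.00 | 0.70 | 94.1% / 69.3% |
| 1.0 | 0.8 | 80 | 73 / 27 | 0.85 | 0.60 | 89.0% / 60.7% |
| 1.0 | 0.8 | 90 | 73 / 27 | 0.93 | 0.65 | 93.3% / 67.8% |
| 1.2 | 0.8 | 80 | 29 / 71 | 0.94 | 0.66 | 89.4% / 61.2% |
| 0.9 | 0.85 | 70 | 109 / -9 | 0.67 | 0.47 | 78.5% / 48.6% |

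The last row is an extreme: Week 12 receives a negative weight. Over s8 from 0.9 to 1.1, ρ from 0.8 to 0.85 and a Week 8 effect of 70% to 90%, the 1000 mg BID estimate runs from 0.67 to 0.95.

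**The case against.** Section 10.4.3 is a one-sentence model description that also omits the covariance structure, and Section 10.1 says a SAP will be finalized before database lock. The endpoint is plainly set at 12 weeks, and applying the same method to week-by-week secondary endpoints makes sense only if visit-specific contrasts were intended. On this view the sentence is incomplete rather than a decision to report a blended effect. That may well be the intention. But the protocol does not leave the model open: it lists the terms and the decision rule. A SAP that follows them inherits the fault, and one that adds the interaction departs from the protocol's stated primary analysis. The SAP was not available here.

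The size and direction have no source in the document, and this stands. Dilution requires an effect still growing after Week 8. The heavy weight on Week 8 requires a smaller SD there; with equal SDs the weights are 50/50, and with a larger Week 8 SD most of the weight moves to Week 12.

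The consequences for testing are modest, and this also stands. With no effect at either visit, the type I error is unaffected. Averaging two visits lowers the variance, so power can rise as well as fall. The study is exploratory, without alpha correction.

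The LOCF ANCOVA would supply a figure close to Week 12, but it is only the sensitivity analysis and does not repair the primary one.

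**Conclusion.** The concern holds. Fitted as listed, the primary MMRM gives one treatment difference averaged over Weeks 8 and 12, while the endpoint and the power calculation refer to Week 12. This follows from the term list and the visit schedule and needs no assumption about effect size.

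How far the estimate misses does rest on assumptions: nothing if the two visits have equal effects, 0.85 for a true 1.0 in the illustrative case, and 0.67 to 0.95 over the stated range. The fault lies in what is estimated, not in validity under the null. The same model also cannot deliver the week-specific secondary comparisons.

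**What to change.** In Section 10.4.3 and the synopsis, add the treatment-by-visit interaction to the MMRM and define the primary result as the least-squares means difference of each dose versus placebo at Week 12. Carry the named visit into the estimand table in Section 10.4.4. For continuous secondary endpoints with repeated visits, state one contrast for each listed week. It is also advisable, though not needed to target Week 12, to add baseline-by-visit and to state an unstructured covariance; the SAP can hold these details.

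The cost is a few words in the protocol and the SAP, with no extra data or subjects. With three arms and two HbA1c visits, treatment-by-visit takes (3 - 1) × (2 - 1) = 2 degrees of freedom and baseline-by-visit 1, so 3 in all. For endpoints with three visits the total is 4 + 2 = 6. The stated 90% and 63% power already refer to a Week 12 comparison, so the sample size need not change.

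### LOCF ANCOVA, the only missing-data sensitivity analysis fixed for HbA1c, does not probe unfavourable departures from MAR; this matters mainly for 500 mg

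*Protocol*

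**What the plan says.** For the primary endpoint, section 10.4.3 states that "the mixed model repeated measures (MMRM) for repeated measurement data is used for analysis". Section 10.1 adds that "The missing values in the raw data are not filled", so the main analysis uses observed HbA1c only. The text does not mention MAR, but an MMRM without imputation relies on it.

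For early withdrawal, the same section continues: "Sensitivity analysis is performed using an analysis of covariance (ANCOVA) model with the last measurement carried forward (LOCF) for subjects who withdrew" before 12 weeks. The synopsis says the same. For the continuous endpoints, the estimand table in section 10.4.4 places LOCF beside the MMRM in the population-level summary: "least-squares means inter-group differences should be calculated using MMRM and the ANCOVA model of LOCF".

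Section 10.1 leaves the detail of missing-value processing in the efficacy sensitivity analyses to the SAP. The protocol names no multiple-imputation, delta-adjusted, tipping-point or reference-based analysis. The per-protocol analysis is a subset analysis, and the failure-type imputation in 10.4.4 applies only to the responder (enumeration) endpoints.

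Section 10.2 plans for appreciable loss: "Given the dropout rate of approximately 20%, 99 subjects are planned to be enrolled in the study (33 subjects in each group").

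**The concern.** A sensitivity analysis of an MMRM should show how far the result depends on the assumption about unobserved outcomes. LOCF imposes one alternative assumption and varies nothing.

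The design makes that assumption hard to interpret. After baseline, HbA1c is scheduled only at Weeks 8 and 12, plus a pre-salvage visit and a withdrawal visit (Study Process table; sections 4.3.6, 4.3.7 and 4.3.9). The carried value is therefore a Week 8, pre-salvage or withdrawal-visit value, standing in for Week 12. Subjects withdrawn for hypoglycaemia, for a contraindication to salvage therapy or for salvage failure leave the study, not only the drug (3.3.1.2, 3.3.2.2). The follow-up at Week 16 is by telephone, with no scheduled HbA1c (4.3.8). No Week 12 value after stopping is planned for these subjects, so the conclusion rests on what is assumed about them. Some of these withdrawals depend on glycaemia, so a departure from MAR is plausible.

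At stake is whether the reported difference, above all for the lower dose in a dose-range-finding trial, would survive a realistic unfavourable assumption. A LOCF result close to the MMRM result could be read as reassurance that it does not give.

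**Working it through.** **Inputs from section 10.2.** Changes of -1.1 (500 mg BID), -1.4 (1000 mg BID) and -0.4 (placebo), so the differences D are 0.7 and 1.0. SD 1.1, two-sided α 0.05, 27 evaluable and 33 enrolled per arm, dropout about 20%.

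**Planned power.** With 27 per arm, SE = 1.1 × √(2/27) = 0.299. The noncentral t distribution with 52 df gives power 0.906 for D = 1.0 and 0.631 for D = 0.7, which reproduces the stated 90% and 63%. Going from 33 to 27 is a loss of 18.2%, in line with a rounded 20%.

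**LOCF difference.** Assume 20% dropout in each arm, with dropouts carrying a share s of their own arm's Week 12 change. The protocol gives neither the timing of dropout nor a Week 8 effect, so s runs over its whole range.

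LOCF difference = 0.8 × D + 0.2 × s × D

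| s | 1000 mg | 500 mg |
|---|---|---|
| 0 | 0.80 | 0.56 |
| 0.5 | 0.90 | 0.63 |
| 0.8 | 0.96 | 0.67 |
| 1 | 1.00 | 0.70 |

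**Reversion of active dropouts to the placebo mean.** 0.8 × D = 0.80 (1000 mg) and 0.56 (500 mg). LOCF may match this or may match the MAR value, depending on an s that nobody sets.

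**Unequal dropout, 500 mg, s = 0.5.**
- 30% active, 10% placebo: active 1.1 × (0.7 + 0.15) = 0.935; placebo 0.4 × (0.9 + 0.05) = 0.38; difference 0.555.
- 10% active, 30% placebo: active 1.1 × (0.9 + 0.05) = 1.045; placebo 0.4 × (0.7 + 0.15) = 0.34; difference 0.705.

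The second exceeds the MAR value of 0.70, so LOCF is not always conservative.

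**Imputed values counted as observed.** With 26.4 completers per arm (33 × 0.8), SE = 1.1 × √(2/26.4) = 0.303. With all 33 counted, and SD held at 1.1, SE = 1.1 × √(2/33) = 0.271. For 500 mg at s = 0.8, the LOCF statistic is 0.672/0.271 = 2.48, against 0.70/0.303 = 2.31 for completers. The check can be easier to pass than the analysis it checks. The MMRM's use of Week 8 data narrows this gap.

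**Shift at which significance is lost.** With the completer-based SE at 20% dropout, the smallest significant difference is about 0.608. A shift δ in active dropouts lowers the difference by 0.2 × δ, so the tipping value is (D - 0.608)/0.2:
- 1000 mg: (1.0 - 0.608)/0.2 = 1.96 HbA1c points.
- 500 mg: (0.7 - 0.608)/0.2 = 0.46 points.

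Full reversion to placebo is a shift of 1.0 for the high dose, well inside 1.96. For the low dose it is 0.7, beyond 0.46, and the resulting 0.56 is below 0.608.

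| Dropout | Smallest significant difference | Tipping shift, 1000 mg | Tipping shift, 500 mg |
|---|---|---|---|
| 10% | 0.572 | 4.28 | 1.28 |
| 20% | 0.608 | 1.96 | 0.46 |
| 30% | 0.652 | 1.16 | 0.16 |

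**The case against.** The strongest reply is that section 10.1 leaves missing-value detail to an SAP that is not shown, and that SAP may add a tipping-point analysis. This stands in part: the absence of such an analysis from the protocol is not in itself an error, and one cannot say that nothing in the trial's plans would reveal a fragile result. But only detail is deferred. The method is already fixed as LOCF in three places, and that choice is open to criticism now.

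It is also fair that the MMRM, not LOCF, is primary, and that the trial is exploratory without alpha correction. This limits the weight of the point but does not make LOCF informative.

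Four stronger readings are tempting, and the documents do not support them:
- **That LOCF fails because it cannot test MAR.** No analysis can, since MAR is untestable from observed data. The defect is that LOCF does not vary departures from it.
- **That LOCF hardly moves the estimate,** say 4% (1.00 to 0.96) against 20% on reversion to placebo. That contrast needs s = 0.8, which is not in the protocol. At s = 0 the two coincide.
- **That LOCF always preserves benefit after stopping.** Subjects who leave for salvage failure or a contraindication to salvage may have HbA1c measured during poor control, because the withdrawal visit repeats the Week 12 procedures. Their carried value may be unfavourable.
- **That the on-treatment analysis adds to this point.** Section 10.4.3 calls it a sensitivity analysis, and the estimand table defines it so that "the on-treatment strategy should be applied, i.e., the data after salvage therapy should also be included in the analysis", the same data rule as the primary strategy. That concerns salvage therapy and is a separate issue.

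**Conclusion.** The point holds as a method fixed badly, of moderate weight. LOCF ANCOVA is the only missing-data sensitivity analysis the protocol names for the primary endpoint, and its relation to the MMRM result depends on an unspecified carried share and on how dropout splits between arms.

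On the planning assumptions the 1000 mg comparison is robust: it survives full reversion of active dropouts to placebo at 10%, 20% and 30% dropout. A reader should not infer that the high-dose conclusion is in danger. The 500 mg comparison, planned at 63% power, is fragile. At 20% dropout a shift of about 0.46 points removes significance, and reversion to placebo gives 0.56 against a threshold of about 0.61.

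These figures assume that the observed differences equal the planned ones, SD 1.1, completer-based standard errors held fixed under the shift, and a shift in the active arm only. The actual MMRM would use Week 8 data and the baseline covariate, so the thresholds are approximate.

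**What to change.** In section 10.4.3, the synopsis and the estimand table in 10.4.4, name a delta-adjusted tipping-point analysis by multiple imputation as the missing-data sensitivity analysis of the MMRM. It should use the same Week 12 model, shift the imputed values of active-arm dropouts, and report for each dose the shift at which significance is lost. A jump-to-reference run, with active dropouts imputed from placebo, is a useful option. LOCF ANCOVA may stay as a supplementary analysis. The imputation details can go in the SAP.

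No new visits or data are needed. The cost is a little programming and a wording change, which as a protocol amendment goes to the Ethics Committee under section 11.6. The sensitivity result for 500 mg may look less favourable.
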